3.3.1 Proposed sample size

This study will enroll a minimum of 360 participants and a maximum of 720 participants.

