8.1 Screening

All PWH who present for care at participating AMC clinical trial sites with a histologically confirmed diagnosis of cancer (within the past 5 years) will be tracked on a screening list. Eligibility will be assessed for each patient on the list, and if they are determined eligible, they will be approached to participate in AMC-115.

To determine the types of cancer cases that present to the clinical sites, all participants presenting at these sites have a minimum set of de-identified data collected. This minimal risk data collection will only include the participant's age, sex at birth, race/ethnicity, and type of cancer and will be performed prior to formal consent. Data collected during screening will be maintained separately from data on enrolled cases. This data will be compared to the total number of enrolled participants at each site to estimate the proportion of participants who consent to participate in this trial.

The protocol chair has established a set of IT logic codes that can be applied to electronic health record (EHR) systems to automate screening for "HIV status" among cancer patients. This is critical as it (1) makes the ascertainment of PWH and cancer uniform across participating domestic AMC sites and (2) reduces physician and study coordinator burden by leveraging the electronic medical record and automating the search. To ensure that this IT-based approach can be implemented across domestic AMC sites, the feasibility survey included a question specifically about the ability of sites to search their electronic medical record systems for HIV-specific disease codes.

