10.1.1 Primary endpoint

The primary endpoint is to estimate the number of cancers in PWH who present for care at domestic AMC sites. These estimates will help to inform the target populations for subsequent AMC clinical trials.

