10.1.2 Primary endpoint analysis

For each cancer group listed below, the number of new and existing cases per month will be estimated using a 95% Poisson confidence interval. Additionally, the distribution of cancer types will be computed as percentages and compared to the cancer type distribution in the HIV/AIDS Cancer Match (HACM) Study, a nationally representative HIV and cancer linkage database [4]. For reference, the HIV/AIDS Cancer Match (HACM) Study estimated that the proportion of participants with the following cancer types as:

1. Solid organ tumors associated with human papillomavirus (HPV) infection = 12.5%
2. Solid organ tumors unrelated to HPV = 49.3%
3. Kaposi sarcoma = 10.9%
4. Hematologic malignancies = 27.3%

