10.2 Sample Size/Accrual Rate

10.2.1 Target accrual is 20 participants per month, with a target of 720 participants enrolled over 36 months. Because the primary objective's focus is estimation, we note below in [Table 10-A](#) both the width of the 95% confidence intervals (CIs) for prevalence, and the accompanying estimated case counts, for the minimum and maximum target sample sizes of 360 and 720. For each cancer group, anticipated prevalence estimates are based on those observed in other national datasets (see [Section 10.1.2](#) above). 95% CIs are computed using PASS 2021 software, utilizing a simple asymptotic estimation approach (i.e., a normal approximation to the binomial approach with a continuity correction.)

Table 10-A: Estimated case counts

Cancer Types	Sample Size of 360		Sample Size of 720	
	Prevalence	Case Count	Prevalence	Case Count
Solid Organ Tumors Associated with HPV	12.5% (95% CI: 8.9-16.1%)	45 cases (95% CI: 32-58 cases)	12.5% (95% CI: 10.0-15.0%)	90 cases (95% CI: 72-108 cases)
Solid Organ Tumors Unrelated to HPV	49.3% (95% CI: 44.0-54.6%)	177 cases (95% CI: 158-197 cases)	49.3% (95% CI: 45.6-53.0%)	355 cases (95% CI: 328-382 cases)
Kaposi Sarcoma	10.9% (95% CI: 7.5-14.3%)	39 cases (95% CI: 27-52 cases)	10.9% (95% CI: 8.6-13.2%)	78 cases (95% CI: 62-95 cases)
Hematologic Malignancies	27.3% (95% CI: 22.6-32.0%)	98 cases (95% CI: 81-115 cases)	27.3% (95% CI: 24.0-30.6%)	197 cases (95% CI: 173-220 cases)

One example of how this will translate into monthly enrollment targets is provided here: If 355 participants with solid organ tumors unrelated to HPV are to be enrolled across 36 months, or 9.9 such participants per month, the 95% CI would be 9.1-10.6 cases (i.e., 9-11 participants) per month.

- 10.2.2. The goal is to open this protocol at $\geq 75\%$ of domestic AMC sites. Based on updated responses from 19 domestic AMC sites on the protocol-associated feasibility survey, 16 AMC domestic sites indicated that this study would be feasible to open. The table below ([Table 10-B](#)) includes results for those 16 domestic sites. Based on their estimates for annual number of cancers seen at their AMC site, we anticipate that this protocol will meet accrual targets.

Table 10-B: AMC domestic site annual numbers of cancers in PWH

AMC Site	Kaposi Sarcoma	Heme Malignancies	HPV+ Solid Tumors	Non-HPV Solid Tumors	Total Cancers
LSUHSC	10	30	10	50	100
Anal Dysplasia Clinic MidWest	0	0	1	0	1
Penn	25	10	10	10	55
Wash U	30	10	15	30	85

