Laser Surgery	2	3	10	0	15
MSK	5	8	5	5	23
Montefiore	2	15	15	15	47
Moffitt	3	20	15	20	58
Boston Medical Center	8	8	15	15	46
Virginia Mason	7	3	4	4	18
Miami Cancer Institute	5	30	25	25	85
George Washington	2	5	10	10	27
Puerto Rico	2	4	4	2	12
UCSF	2	1	5	3	11
UCSD	32	59	23	52	166
UNC	4	4	2	4	14
Total	139	210	169	245	763

The above estimates indicate that sites, including those with a history of consistent enrollment onto AMC trials and new sites added in current AMC grant years, see 763 cancer cases with underlying HIV infection each year. Even with a conservative patient participation rate for this minimal burden study, the protocol chairs deem the target accrual range (360-720) to be feasible.

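### The primary count of presenting cancers has no named data source or exposure time, and its new/existing split can be computed only from consented enrollees

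*Combined protocol and SAP*

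**What the plan says.** Section 10.1.1 sets the target: "The primary endpoint is to estimate the number of cancers in PWH who present for care at domestic AMC sites". Table 9-A, written for the same objective, also counts people who come to the site and splits them into primary, recurrent and prior cases. For the analysis, Section 10.1.2 states that for each of four cancer groups "the number of new and existing cases per month will be estimated using a 95% Poisson confidence interval". It does not say whether the cases come from the screening list or the enrolled set, or over what observation time.

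The planning works from enrollment. Section 3.3.1: "This study will enroll a minimum of 360 participants and a maximum of 720 participants". Section 10.2.1: "Target accrual is 20 participants per month, with a target of 720 participants enrolled over 36 months". Table 10-A gives expected counts and 95% intervals for 360 and 720 enrollees. One count is then turned into a monthly figure, offered as an illustration of enrollment goals: "If 355 participants with solid organ tumors unrelated to HPV are to be enrolled across 36 months, or 9.9 such participants per month", with an interval of 9.1-10.6.

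Section 8.1 sets up a second source: a list of all people with HIV and cancer who present, without a cap, meant to show which cancer types present. The data taken from them are limited to "age, sex at birth, race/ethnicity, and type of cancer and will be performed prior to formal consent". One calculation is given for these data: "This data will be compared to the total number of enrolled participants at each site to estimate the proportion of participants who consent". Section 12.1 adds that nothing further is recorded for anyone who declines.

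Below Table 10-B, the plan says that the 16 sites that judged the study feasible "see 763 cancer cases with underlying HIV infection each year".

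**The concern.** The target is a number presenting. A count of enrollees is a different quantity: it depends on who is approached, who agrees, and when accrual stops. If the monthly figures come from enrollees, they understate the number presenting by the non-consent fraction, and by the cap where it binds. A Poisson interval describes random variation in the count and does not cover that shortfall.

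Section 10.1.1 says that the estimates will guide the choice of target populations for later consortium trials. A figure read as caseload that is really caseload times consent would understate how many patients a future trial could draw on. If consent differs by cancer group, it would also distort the comparison between groups.

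**Working it through.** **1. Reproduce the plan's example.** Inputs from Sections 10.1.2 and 10.2.1: share p = 0.493, n = 720, 36 months, normal approximation with continuity correction.

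- Half-width = 1.96 × √(0.493 × 0.507 / 720) + 1/(2 × 720) = 0.0365 + 0.0007 = 0.0372.
- Share: 45.58% to 53.02%. Times 720: 328.2 to 381.8 cases. Divided by 36: 9.12 to 10.60 per month.

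This matches the stated 9.1-10.6, and the other Table 10-A intervals reproduce within rounding in the same way. The monthly figure is therefore 720 × 0.493 / 36: the enrollment target times an external share.

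**2. What that construction implies.** The four shares sum to 100%, so the group figures must total 720/36 = 20.0 per month at the maximum and 360/36 = 10.0 at the minimum. Doubling the enrollment target doubles the planned monthly cases with no change in burden.

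**3. Compare with the interval that 10.1.2 names.** Exact Poisson limits for x = 355 over 36 months:

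- Lower: χ²(0.025; 710) / 2 / 36 = 8.86.
- Upper: χ²(0.975; 712) / 2 / 36 = 10.94.

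The width is 2.08, against 1.49 for the binomial interval, which treats n as fixed. It is about 40% wider.

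**4. Which source can supply the primary analysis?**

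| Needed | Screening list (8.1, 12.1) | Enrolled set (8.2) |
|---|---|---|
| Cancer group | Yes | Yes |
| New or existing status | No | Yes (8.2.6) |
| Month of presentation | Not among the permitted fields | Month of registration only |
| Everyone who presents | Yes, if histologically confirmed | Only those who consent, up to 720 |

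Neither source meets all four needs. The list could give counts by cancer type. The new/existing count and the Table 9-A split can come only from enrollees.

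**5. Scale.** Table 10-B gives 763/12 = 63.6 cases per month. Enrollment at the maximum is 20/63.6 = 31% of that; at the minimum it is 10/63.6 = 16%.

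**6. When the cap binds.** The plan gives no participation rate, and Table 10-B does not say whether the same patients recur from year to year. The two extremes are:

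- All yearly cases distinct: 3 × 763 = 2,289 in 36 months. The cap binds above 720/2,289, about 31% participation.
- The same 763 patients every year: the cap binds only above 720/763, about 94%. In that case 763/36 = 21.2 distinct people present per month, and 360 enrollees would be 360/763 = 47% of them.

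Below the cap the count is still burden times consent. With distinct cases and 10% participation, 229 enroll, or 229/36 = 6.4 per month against 63.6 presenting.

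**The case against.** The example in 10.2.1 is not the primary analysis. It is presented as an enrollment illustration, and 10.1.2 does not say that enrollees are the numerator or that 36 calendar months is the divisor. Table 9-A speaks of people who present, and the stated purpose of the uncapped list is close to the primary objective. A reasonable reader could take the list as the intended source. For counts by cancer type this objection stands: the list could supply them if the plan said so. It does not rescue the new/existing count, because Sections 8.1 and 12.1 keep that status off the list.

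Table 10-B also holds informal site estimates, and any feasible accrual plan enrolls fewer than the caseload. That stands too: 31% and 16% indicate scale and do not measure the bias of a specified estimator. It would be wrong to set the 9.9 per month for non-HPV solid tumors against the survey's 245/12 = 20.4, because the first uses a 49.3% reference share and the second a survey share of 245/763 = 32.1%. That contrast mixes case mix with enrollment.

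Finally, the list is not a perfect census. Section 8.1 restricts it to histologically confirmed cancer, while Section 3.1.3 has no such limit and Section 8.2.7 allows clinical or cytologic diagnosis. Moving the count to the list without resolving this would miss some cases.

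**Conclusion.** The point holds. The numerator and exposure time of the primary analysis are unspecified, precision is planned on enrollees, and as written the new/existing count can be computed only from consented participants. That count estimates burden times consent rate, limited to 720, and not the number presenting.

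The size depends on unstated participation and on repeat patients. At maximum enrollment the count would be between 31% (all yearly cases distinct) and 94% (the same patients each year) of the people presenting; at the minimum, between 16% and 47%. Both ranges take Table 10-B at face value. Separately, the example interval is narrower than the Poisson interval that the plan names (9.1-10.6 against about 8.9-10.9).

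A reader might infer that the trial will simply report its accrual target as the cancer burden. The documents do not support that: 10.1.2 names no source, an uncapped list exists, and with low participation consent rather than the cap would set the count. Sites opening at different times would also matter if counts were divided by 36 calendar months, but the plan gives neither that divisor nor an opening schedule, so no size can be attached.

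**What to change.** - In 10.1.2, take the monthly counts and the cancer-type distribution from the screening list, with each person counted once per site and site-months of active screening as exposure.
- Add two fields to the minimum dataset in 8.1 and 12.1: cancer status (new, recurrent, prior or in remission) and month of first presentation.
- If these cannot be added, report list counts by cancer type only and label the new/existing split as describing enrollees.
- Reconcile the list's histologic restriction with eligibility and with 8.2.7.
- Relabel Table 10-A as precision for the enrolled sample, and give Poisson intervals for the monthly counts.

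The cost is a protocol amendment with CIRB approval and brief extra chart abstraction per screened patient. The CIRB would have to accept both fields within the de-identified, minimal-risk basis of the pre-consent collection. Duplicates across sites would probably remain, which is why the count is per site. No extra participants are needed. The change should come early, since status not recorded at screening may not be recoverable for people who decline.

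### The case-count and monthly confidence intervals in Section 10.2.1 are binomial with total enrollment fixed, so they are narrower than the Poisson intervals planned in Section 10.1.2, and their case mix differs from the site survey in three of four groups

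*Combined protocol and SAP*

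**What the plan says.** Section 10.1.2 sets the primary analysis: for each of four cancer groups, "the number of new and existing cases per month will be estimated using a 95% Poisson confidence interval". It adds a second output, the percentage distribution of cancer types compared with the national HIV/AIDS Cancer Match (HACM) figures.

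Section 10.2.1 justifies the sample size by precision alone, "for the minimum and maximum target sample sizes of 360 and 720". It names the method openly as "a normal approximation to the binomial approach with a continuity correction". Table 10-A gives a percentage with its interval and a case count with its interval for each group. A worked example then converts one count to a monthly figure: with 355 solid tumors unrelated to HPV over 36 months, "the 95% CI would be 9.1-10.6 cases (i.e., 9-11 participants) per month". The time base is explicit: "Target accrual is 20 participants per month, with a target of 720 participants enrolled over 36 months".

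On the source of the mix, Section 10.2.1 says that "anticipated prevalence estimates are based on those observed in other national datasets". The shares are 12.5% HPV-related solid, 49.3% non-HPV solid, 10.9% Kaposi sarcoma and 27.3% hematologic. Section 10.2.2 and Table 10-B then report a survey of the 16 sites that found the study feasible, and use it to argue that accrual will be met ("Based on their estimates for annual number of cancers seen at their AMC site"). The plan does not comment on the difference between the two mixes and gives no Poisson-based precision.

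**The concern.** The primary objective is estimation, so the interval widths in Section 10.2.1 are the whole statistical case for 360 to 720 participants. Those widths should be the ones that the primary analysis will produce. A binomial interval treats total enrollment as known and asks only how it divides among groups; the variance of a group count is then np(1-p). A Poisson interval treats the group count itself as random, with variance np. The gap grows with the group's share, so it is largest for the group chosen as the worked example.

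The second matter is the center of the intervals. Table 10-A and Table 10-B stand next to each other and imply different numbers of cases per group. A reader who plans later trials from Table 10-A would expect more non-HPV solid tumors, and fewer HPV-related tumors and Kaposi sarcomas, than the sites' own figures suggest.

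**Working it through.** **Inputs.** Shares from Section 10.1.2; n = 360 and 720, and 36 months, from Section 10.2.1; survey totals from the last row of Table 10-B (139 Kaposi sarcoma, 210 hematologic, 169 HPV-related, 245 non-HPV, 763 in all). The rows and columns of Table 10-B add up correctly.

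**Step 1: reproduce the stated figure.** The formula is p ± [1.96·√(p(1-p)/n) + 1/(2n)]. For p = 0.493 and n = 720:
- 1.96·√(0.493 × 0.507/720) = 0.0365, and 1/(2 × 720) = 0.0007, so the half-width is 0.0372.
- The share is 45.6-53.0%.
- Multiplied by 720, the count is 328.2-381.8.
- Divided by 36, the monthly figure is 9.12-10.60, the stated 9.1-10.6.

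The other intervals in Table 10-A reproduce in the same way to within one unit of rounding (largest gap: Kaposi sarcoma at n = 360, upper limit 51.3 computed against 52 stated).

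**Step 2: apply the planned method.** The exact Poisson limits for x cases are χ²(0.025; 2x)/2 and χ²(0.975; 2x+2)/2. For x = 355 they are 319.0 and 393.9, and division by 36 gives 8.86-10.94 per month. At n = 720:

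| Group | Cases | Stated interval | Exact Poisson | Width ratio |
|---|---|---|---|---|
| Non-HPV solid | 355 | 328-382 | 319-394 | 1.40 |
| Hematologic | 197 | 173-220 | 170-227 | 1.17 |
| HPV-related solid | 90 | 72-108 | 72-111 | 1.07 |
| Kaposi sarcoma | 78 | 62-95 | 62-97 | 1.06 |

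The ratios follow from 1/√(1-p): 1.404, 1.173, 1.069 and 1.059. They are nearly the same at n = 360, where the non-HPV interval is 152-205 against the stated 158-197.

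**Step 3: apply the survey mix.** Survey share = column total/763; expected count = 720 × share. This assumes equal participation in every cancer group, which the documents neither state nor support with data.

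| Group | Planning share | Survey share | Table 10-A count | Survey-mix count | Difference |
|---|---|---|---|---|---|
| Non-HPV solid | 49.3% | 32.1% | 355 | 231 | -35% |
| HPV-related solid | 12.5% | 22.1% | 90 | 159 | +77% |
| Kaposi sarcoma | 10.9% | 18.2% | 78 | 131 | +68% |
| Hematologic | 27.3% | 27.5% | 197 | 198 | +1% |

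For non-HPV solid tumors, 231/36 = 6.4 per month, with exact Poisson limits 202-263 cases, or 5.6-7.3 per month.

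**Step 4: what the planning mix would require.** Take the survey at face value for three years: 3 × 245 = 735 non-HPV, 3 × 169 = 507 HPV-related, 3 × 139 = 417 Kaposi sarcoma and 3 × 210 = 630 hematologic cases seen. The Table 10-A counts then need participation of 355/735 = 48%, 90/507 = 18%, 78/417 = 19% and 197/630 = 31%. So the non-HPV count runs from about 231 with equal participation to 355 with participation as unequal as this.

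**The case against.** A reader might infer that Table 10-A is miscalculated. It is not. The method is disclosed, the figures reproduce, and binomial intervals are right for the percentage columns, which serve the planned comparison with the national distribution. The mismatch is confined to the count columns and the monthly example.

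The binomial model can also be defended for counts, because enrollment is capped at 720 and, given a fixed total, group counts are multinomial. This limits the weight of the point. It does not remove it, since Section 10.1.2 commits to a Poisson interval and the monthly example is the quantity to which that interval applies. A related limit is that the primary endpoint concerns patients who present for care, and Section 8.1 puts them all on a screening list. If the Poisson count is taken from that list, 355 is not its expected value. The interval 319-394 is the Poisson counterpart of the protocol's own example, not a forecast.

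The practical effect on the example is small: 8.9-10.9 still rounds to 9-11 per month, and two of the four groups widen by only 6-7%.

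A reader might also infer that the survey contradicts the planning mix and that monthly group targets must be reset. The documents do not support that. Table 10-B holds site estimates of cases seen, not enrolled; one site supplies 166 of the 763; hematologic malignancies agree; and HACM is the prespecified comparator, so planning on it is coherent. The protocol describes its example as showing monthly enrollment targets, but it sets no cancer-group quota. What stands is that the plan has two mixes and gives precision for only one.

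**Conclusion.** The point holds on both parts, with modest weight. The count and monthly intervals in Section 10.2.1 are not those that the planned primary analysis would give: at 720 participants the Poisson intervals are wider by about 40%, 17%, 7% and 6% (non-HPV, hematologic, HPV-related, Kaposi sarcoma). This rests only on the plan's own shares, sample sizes and stated method.

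The case-mix difference has the larger numerical effect but the weaker footing. Three of four groups would fall outside the Table 10-A count intervals under the survey mix, and this depends on equal participation across groups and on site estimates of cases seen. It shows that the planned counts are sensitive to the assumed mix, not that either mix is wrong. Neither part affects the validity of the study or calls for a different sample size.

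**What to change.** 1. Restate the case-count intervals in Table 10-A and the monthly example with Poisson limits: for the example, 319-394 cases, or 8.9-10.9 per month.
2. Keep the binomial intervals for the percentage columns, and label those columns as shares of cases rather than prevalence.
3. Add a sensitivity panel with the Table 10-B mix (231, 159, 131 and 198 cases at n = 720, with Poisson limits), and state the equal-participation assumption beside it.

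The cost is recalculation and table text, and slightly less favorable stated precision. No new cancer-group targets and no change to the 360-720 range are needed.

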10.3 Analysis of Secondary Endpoint and Analysis

The secondary endpoint is the proportion of participants eligible for AMC trials who are successfully enrolled.

For this calculation, the denominator will be computed based on PWH deemed eligible at each site, based only on AMC trials open at that respective site.

For participants with active disease, each participant's data will be evaluated to determine whether they meet minimal eligibility criteria for an AMC clinical trial open at

their respective domestic site, defined as meeting the following minimum eligibility criteria per the protocol:

- a. Cancer diagnosis including stage and histology
- b. Age range specified in the protocol for which the patient is being screened
- c. Indication for the study intervention (e.g., symptom, toxicity)

These data will be compared to the actual number of participants enrolled onto AMC trials open at each site to estimate the proportion of trial-eligible participants who enroll. For participants with a history of malignancy diagnosed within the past 5 years / cancer currently in remission, each patient's performance status and HIV metrics (CD4+ T-cell count and HIV viral load) will be evaluated to determine whether they meet general levels that are consistent with eligibility criteria for prior AMC clinical trials. To characterize participants who are eligible but not enrolled onto AMC trials, participant characteristics for eligible participants will be compared according to successful enrollment versus not using two-sample tests for continuous and categorical data (e.g., t-test, Wilcoxon rank sum test, chi-square test). Characteristics will include demographic features, clinical/cancer features, and optional QOL responses.

EORTC QLQ-C30 subscale and overall scores will be used to describe participant symptom and health-related quality of life burden. SNSCS-SF34 scores will be used to categorize participants based on the degree to which their needs are met. Baseline EORTC QLQ-C30 and SCNS-SF34 scores will also be compared according to successful enrollment versus not using t-test or Wilcoxon rank sum tests depending on distribution of scores. These data may describe enrollment barriers previously unknown. For example, comorbidity burden, prior cancer treatment history, or self-reported quality of life at initial cancer presentation may be risk factors for elective participation. These analyses will provide preliminary data to inform evidence-based interventions aimed at increasing clinical trials participation among PWH at domestic AMC sites. To address minority and underserved populations, additional analyses will examine the interaction with race, ethnicity, socioeconomic status, and health insurance status to compare participant characteristics according to groups defined by enrollment status and these variables. Similarly, interactions with age, cancer type, treatment, and time since diagnosis will be investigated. Finally, these analyses will inform a multivariable logistic model that predicts successful trial outcome that includes dependent variables for participant characteristics; interactions with indicators of minority, socioeconomic status, and health insurance will be investigated in this model as well as with age, cancer type, treatment and time since diagnosis.

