8.2 Enrollment Data Collection

Following informed consent, additional, identifiable data will be collected, including:

- 8.2.1 Patient characteristics: Date of birth, biological sex, gender identity, race, ethnicity, height and weight
- 8.2.2 Sociodemographic: Socioeconomic status (e.g., ZIP code, housing status [homeless y/n, categories for frequency of housing insecurity]), health insurance (insured/uninsured, type if insured)
- 8.2.3 Health behaviors: Tobacco use (type, exposure [pack/day, years use]), illicit drug use (ever, type, years exposure), alcohol use (ever, exposure [drinks/week], years exposure)
- 8.2.4 Comorbid conditions: Hepatitis B and C co-infection, cardiovascular disease (y/n, type), psychiatric conditions (y/n, type), non-cancer pulmonary conditions (y/n, type), hepatic dysfunction, hematologic abnormalities, renal dysfunction, neurologic disorders, endocrine disorders (including thyroid disorders, and diabetes)
- 8.2.5 HIV care: Current ART regimen, years of ART use, year of HIV diagnosis, history of opportunistic infections, most recent HIV viral load and CD4+T-cell count relative to participant visit).

8.2.6 Status of cancer diagnosis (one of the following):

- New diagnosis, pre-treatment phase
- New diagnosis, treatment phase
- Prior diagnosis, in remission (within 5 years of initial diagnosis or treatment)
- Prior diagnosis, recurrent, pre-treatment phase
- Prior diagnosis, recurrent, treatment phase
- Prior diagnosis, recurrent, no treatment planned

8.2.7 For participants with a new diagnosis (pre-treatment or treatment), the following will be collected:

- Cancer type, date of cancer diagnosis, method of diagnosis (clinical, cytology, histology), type of pathology performed (Hematoxylin and Eosin, immunohistochemistry, other), date of pathology, staging, staging methods (clinical, radiographic, surgical), date(s) of staging, current ECOG Performance Status (PS), current laboratory values (this would include complete blood count, renal and liver function, electrolytes)
- Cancer treatment plan: Detailed planned or current treatment. This should encompass surgical interventions, radiotherapy, and chemotherapy (agent names), including dates of planned or current therapy, and whether cancer care is being received or will occur at the enrolling institution.

8.2.8 For participants with a prior diagnosis in remission, the following will be collected:

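### The active-disease eligibility denominator in Section 10.3 omits performance-status, laboratory and HIV limits, so the eligible-but-not-enrolled group can include patients whom the open trial would have excluded

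*Combined protocol and SAP*

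**What the plan says.** Section 10.3 defines the endpoint: "The secondary endpoint is the proportion of participants eligible for AMC trials who are successfully enrolled". It adds that "the denominator will be computed based on PWH deemed eligible at each site, based only on AMC trials open at that respective site".

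For active disease, each participant's data are used to "determine whether they meet minimal eligibility criteria for an AMC clinical trial open at" their site, and three items decide this:
- "Cancer diagnosis including stage and histology"
- the age range of the trial in question
- the indication for the study intervention

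Section 10.3 calls these criteria minimal, but then refers to the resulting group as trial-eligible.

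For participants in remission the rule differs. Their "performance status and HIV metrics (CD4+ T-cell count and HIV viral load) will be evaluated to determine whether they meet general levels" in line with the criteria of prior AMC trials.

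Eligible participants are then compared by enrollment status on demographic features, clinical and cancer features, and QOL, using two-sample tests. The results feed a multivariable logistic model. As an example of what may emerge, the section says that "comorbidity burden, prior cancer treatment history, or self-reported quality of life at initial cancer presentation may be risk factors for elective participation".

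Section 8.2 already collects most of what a fuller check needs. ECOG performance status and "current laboratory values (this would include complete blood count, renal and liver function, electrolytes") are recorded for new diagnoses (8.2.7) and recurrent disease (8.2.9). The most recent viral load and CD4 count are recorded under 8.2.5. Table 2-A records clinical trial enrollment and trial details.

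**The concern.** The secondary objective (Section 1.2.1) is to characterize people who were eligible but did not enroll, in order to understand accrual barriers. That requires knowing who could have enrolled. Someone who matches an open trial on diagnosis, age and indication but fails its performance-status, organ-function or HIV limits had no choice to make. Under Section 10.3 that person is still counted as eligible and not enrolled.

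Two results are affected. The enrolled proportion is lower than the proportion among people who could have enrolled. The enrolled-versus-not contrasts also pick up characteristics that go with exclusion, such as comorbidity, poor function and poor QOL. Those are among the characteristics that the section suggests may bear on elective participation.

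No listed data item separates the possibilities. Reasons are collected for planned therapy that did not start (Section 2.2, 12-week follow-up), but not for non-enrollment in a trial. Section 2.2 names people who elect not to screen and people screened but found ineligible as distinct groups of interest; Section 10.3 does not keep them apart.

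**Working it through.** The documents give no expected value, precision or power for the secondary endpoint, so there is no stated figure to reproduce. The steps below show the direction of the effect and its size over assumed ranges.

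**Step 1. Which criteria are applied to whom (Section 10.3) and what is collected (Section 8.2).**

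| Item | Active disease: applied | Remission: applied | Active disease: collected |
|---|---|---|---|
| Diagnosis, stage, histology | yes, open trials | not stated | yes |
| Age | yes, open trials | not stated | yes |
| Indication | yes, open trials | not stated | not listed as such |
| Performance status | no | yes, prior trials | yes (8.2.7, 8.2.9) |
| CD4, viral load | no | yes, prior trials | yes (8.2.5) |
| Blood count, renal, liver | no | no | yes (8.2.7, 8.2.9) |

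**Step 2. Effect on the proportion.** Let π be the enrollment proportion among the fully eligible, and f the share of the three-criteria denominator that fails the open trial's other limits. Assume that nobody who fails them enrolls.

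- Reported proportion = π(1 − f)
- Share of eligible non-enrollers who are in fact ineligible = f / [1 − π(1 − f)]

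Neither π nor f is in the documents. Over assumed ranges:

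| π | f | Reported proportion | Ineligible share of non-enrollers |
|---|---|---|---|
| 20% | 10% | 18% | 12% |
| 20% | 20% | 16% | 24% |
| 20% | 40% | 12% | 45% |
| 40% | 10% | 36% | 16% |
| 40% | 30% | 28% | 42% |
| 60% | 50% | 30% | 71% |

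For example, at π = 20% and f = 20%: 0.20 × 0.80 = 0.16, and 0.20 / (1 − 0.16) = 0.24.

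**Step 3. Effect on the group comparison.** All inputs are assumed: 200 people in the denominator, poor performance status in 10% of the fully eligible and 50% of the ineligible, and no relation between performance status and enrollment among the fully eligible.

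At f = 20% and π = 50% there are 160 fully eligible people, of whom 80 enroll. Non-enrollers number 80 + 40 = 120. Poor performance status among them is (80 × 0.10 + 40 × 0.50) / 120 = 28/120 = 23%, against 10% in enrollees. The odds ratio is (0.233/0.767) / (0.10/0.90) = 2.7.

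| f | π | Poor status, non-enrollers | OR | Chance of p < 0.05 (two-sided) |
|---|---|---|---|---|
| 10% | 30% | 15.5% | 1.65 | about 15% |
| 20% | 50% | 23% | 2.7 | about 69% |
| 30% | 50% | 28.5% | 3.6 | about 89% |

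A difference thus appears with no preference effect at all, but its size and detectability vary widely with the inputs.

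**The case against.** **The broad denominator is disclosed and may be partly deliberate.** The criteria are openly called minimal, and restrictive entry criteria are themselves a trial-specific barrier, which the objective covers. If the target is enrollment among patients with a matching open trial, the three-criteria proportion is the right quantity. This stands. It is a reason to keep that proportion and label it accurately. It does not justify calling the group trial-eligible or leaving the excluded unseparated.

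**The reading as elective participation is hedged.** It is one example, in analyses described as preliminary. Performance status or CD4 could be compared as clinical features, so a gradient would be visible. That also stands, but comparing a feature by enrollment status does not show whether it acted through choice or through exclusion.

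**Collected values may be badly timed.** They are current at AMC-115 registration, and Section 8.2.6 admits treatment-phase participants, so they may postdate a trial decision. Section 8.2.11 allows viral load and/or CD4, so one may be missing. This stands and the fix must handle it.

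**Stronger readings that a reader might infer:**
- *That the plan applies all the omitted criteria, laboratory values included, to the remission group.* It does not: laboratory values are applied to nobody, and 8.2.8 does not list current values for remission.
- *That remission participants are placed in the denominator on prior-trial criteria.* Section 10.3 limits the denominator to open trials and describes the prior-trial assessment without saying that it feeds the denominator. This is an ambiguity, not a stated rule.
- *That a large, significant artefact is to be expected.* Take 400 minimally eligible, 20% with ECOG 2 or worse, 70% of those failing a performance-status limit, and 20% enrollment among the rest. Enrollment is then 4.8/80 against 64/320, OR 0.26, chi-square p = 0.003. But every input is assumed, and 400 exceeds the 360 minimum sample. With 150 the p-value is 0.07; with 400 but 30% failing, the OR is 0.65 and p = 0.22.

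**Conclusion.** The point holds for the secondary analysis. The plan calls active-disease participants trial-eligible on three criteria, compares them by enrollment status, and cannot tell refusal or lack of an offer from exclusion, although data for a fuller check are largely collected.

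Relative to enrollment among the fully eligible, the reported proportion is too low by the factor (1 − f) whenever f exceeds zero. This assumes that people failing the limits do not enroll. The size cannot be computed, because the open trials' limits and failure rates are not in the documents; 16% to 12% for a true 20% (f = 20% to 40%) is an illustration only. Health-related contrasts are partly confounded with ineligibility to the extent that those features track the limits.

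The documents do not support calling the three-criteria proportion wrong in itself, nor saying that the plan commits to reading sicker patients as unwilling. The primary endpoint is not affected.

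**What to change.** 1. Keep the three-criteria proportion, but label it potentially eligible.
2. Add a second proportion that also applies each open trial's performance-status, laboratory and CD4/viral-load limits to the values collected under Section 8.2.
3. Report a three-way split: not eligible on collected criteria; eligible, not enrolled; enrolled. Run the enrolled-versus-not comparison and the logistic model on the last two groups, and show the three-criteria version alongside.
4. Count actual trial enrollees as eligible, whatever their values at AMC-115 registration.
5. For treatment-phase participants, use values dated before the trial decision where available, and otherwise classify them as undetermined. Do the same when a needed CD4 or viral load is missing. Report the number undetermined.
6. State that remission participants enter the denominator only if a trial open at the site takes such patients, and report their prior-trial assessment separately.

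An optional addition is a data item for the reason for non-enrollment (declined, not offered, screen-failed). The split above removes known ineligibility but still leaves refusals and missing offers together.

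Cost: SAP wording, programming, and a site-by-date table of open-trial criteria. The fully eligible group will be smaller, and some cases will stay undetermined. The optional item would need a form change.
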